### **11.3 Expedited Reporting**

The Sponsor will report all relevant information about SUSARs that are fatal or life-threatening as soon as possible to the FDA and in any case no later than 7 days after knowledge by the Sponsor/designee of such a case, and the relevant follow-up information will subsequently be communicated within an additional 8 days.

All other SUSARs will be reported to the FDA as soon as possible but within a maximum of 15 days of first knowledge by the Sponsor/designee.

The Sponsor/designee will also inform all Investigators as required.

### **11.4 Clinical Laboratory Evaluations**

Safety laboratory tests will include chemistry, hematology, and urinalysis. See [Appendix I](#) for a complete list of analytes. Chemistry laboratory tests will be collected after a minimum 8- to 10-hour fast.

Safety laboratory tests will be evaluated at the times indicated in the Schedule of Assessments table.

Abnormal Screening laboratory values that appear to be spurious (eg, laboratory error), or that are the result of an identified transient event that if resolved is unlikely to recur, may be repeated once. Should this occur, the Investigator should document the reason for repeating the test.

If, in the opinion of the Investigator, any patient has a clinically significant abnormal laboratory finding in comparison to the value at the time of randomization or unresolved TEAEs, additional follow-up visits will be scheduled. Patients will be followed approximately once a week (or more frequently as deemed appropriate) until the Investigator determines that repeat laboratory findings are clinically unremarkable in comparison to baseline, or unresolved AEs return to prestudy levels or clinically acceptable levels.

If a patient experiences an SAE for which follow-up laboratories and review are required, the Investigator will schedule additional post dose visits as necessary.

If, in the opinion of the Investigator, any patient has a clinically significant AE at the follow-up call, the Investigator will provide additional follow-up until the AE returns to clinically acceptable levels.

The safety laboratory sample collection times may be refined based on emerging data to ensure study objectives are met.

### **11.5 Vital Signs**

Vital signs, including heart rate, blood pressure, respiration rate, and temperature, will be measured at the times indicated in the schedule of assessments ([Table 1](#)) using the following standardized procedures:

- Prior to measuring vital signs, the patient should be sitting for a minimum of 5 minutes with his/her back supported, feet flat on the floor, and his/her measurement arm supported so that the midpoint of the manometer cuff is at heart level.
- Standing pulse and blood pressure will be obtained following sitting vital signs.
- An appropriately sized cuff should be used with the bladder centered over the brachial artery.
- The cuff size and arm used for the measurement should be recorded. Whenever possible, the same arm should be used for all vital sign assessments throughout the study.
- Blood pressure should be recorded to the nearest whole number on an automatic device.

### **11.6      Electrocardiograms**

Twelve-lead ECGs will be performed at the times indicated in the Schedule of Assessments table. Every effort will be made to eliminate any sources of physical (including any movement, eating, or drinking) or electrical interference. During these assessments, patients are not permitted to use cell phones, iPods, laptop computers, tablets, or any type of battery-operated or electrical device, and all of these devices must be turned off during the assessments.

All 12-lead ECGs will be performed with the patient resting in the supine position. Twelve-lead ECGs will be printed and all ECGs must be evaluated for the presence of abnormalities by a qualified physician. A digital recording of all ECGs for randomized patients will be submitted to a central reviewer. In the case of a disagreement between the local (site) reading and the central overread, the central overread interpretation of the ECG data will be utilized for all safety analyses.

Standard ECG parameters will be measured, and the following ECG parameters will be recorded:

- QRS interval
- Heart rate
- RR interval
- QT interval
- QTc (QTcF)

Investigators should contact the Sponsor or designee if any clinically meaningful changes from baseline are noted on review.

### **11.7      Physical Examinations**

A comprehensive physical examination will be performed at Screening. A comprehensive physical examination will consist of general appearance, skin, HEENT, chest (including heart/lungs), abdomen (including liver/kidneys), musculoskeletal, sensory/neurological.

Subsequent directed physical examinations will be performed at the times indicated in the Schedule of Assessments table. The directed physical examination will assess changes from the prior visit or new concerns.

Assessment of skin integrity and wound healing, if applicable, will also be performed at the times indicated in the Schedule of Assessments table. Skin breaches and wounds will be examined and

the following parameters recorded: location, size, depth, and evidence of erythema, edema, warmth, odor, or drainage.

All complete and limited physical examination findings must be recorded.

### **11.8 Height and Weight**

Height and weight will be measured at the times indicated in the schedule of assessments ([Table 1](#)) and will be used to calculate BMI. Height will be measured with the patient's shoes off.

Weight will be measured with the patient's shoes off and after the patient's bladder has been emptied.

### **11.9 Safety Data and Potential Risks**

Toxicology studies have been conducted in rats (up to 6 months) and dogs (up to 9 months), and in both species the results support the use of ricolinostat during acute and chronic dosing. The study report from the rat 6-month study reported 'no ACY-1215-related macroscopic findings, organ weight changes, and microscopic findings at the Day 91 interim and Day 181/182 terminal sacrifice were noted. At the highest exposure observed in the chronic toxicology study in dogs, at study endpoint changes in some hematologic and clinical chemistry parameters were noted. Most of these changes remained within normal historical ranges, and all are monitorable in humans. Detailed descriptions of the design and results of these studies can be found in the Investigator's Brochure.

With respect to human data, clinical studies of ricolinostat have been conducted in 229 patients with multiple myeloma as described in Section [5.4](#) of this protocol and in the Investigator's Brochure. In these studies, ricolinostat was administered at doses from 40 mg to 360 mg as monotherapy or in combination with chemotherapy for extended periods, with a maximum treatment duration in the monotherapy study of 29.5 weeks and a maximum treatment duration of 174 weeks (~3.3 years) in combination studies. Details of the overall safety profile from these studies are provided in the Investigator's Brochure and above (see Section [5.4](#)). Detailed safety results and descriptions of SAEs are also available in the Investigator's Brochure. Briefly, the observed SAEs were consistent with the serious underlying illness and poor health status of the study populations and did not suggest safety concerns attributable to ricolinostat. Similarly, the observed AEs or laboratory changes in the monotherapy as well as the combination studies, including episodes of neutropenia, anemia and changes in renal function in some patients, appeared to be consistent with the underlying malignancy and general health status of the patients and the known profiles of the chemotherapeutic agents being administered concurrently rather than attributable to ricolinostat.

No deaths occurred in healthy volunteers who received ricolinostat. Among the 229 individuals with refractory multiple myeloma treated with ricolinostat, 11 (5%) deaths occurred, of which 1 was in the monotherapy study and 10 were in the combination studies. No clear dose relationship to ricolinostat was observed, and all deaths occurred in patients who were ill with advanced

multiple myeloma. The causes of death were attributed to several different events: cardiac arrest/sudden death (N=2), pulmonary embolism (N=2), sepsis/septic shock (N=3), pneumonia (N=2), bacterial meningitis (N=1), and ‘mental status changes,’ with a number of terminal events described in the narrative (N=1). None of these deaths was judged by the assessing Investigator as likely due to treatment with ricolinostat, and all were consistent with the severe and progressive underlying neoplastic disease (refractory multiple myeloma) of the patients being studied. Further details are available in the Investigator’s Brochure.

In the one healthy volunteer study conducted to date, the most common adverse effect reported in a study of healthy volunteers administered ricolinostat doses of 120 and 160 mg in crossover fashion was throat irritation (3 patients), and no SAEs were reported.

As described above, the overall body of safety data does not predict serious safety concerns specific to ricolinostat. However, as a result of their underlying disorder, patients with diabetes are at increased risk for a number of medical problems such as renal impairment and increased risk for infections. The available data do not suggest that ricolinostat is likely to increase these risks, but it is important to monitor these issues, and therefore the protocol will include specific monitoring for several potential AEs and laboratory changes designated as events of special interest and described in Section 11.10.2.2 below. Finally, with respect to skin biopsy, although patients with diabetes are at increased risk for poor wound healing related to vascular disease, the skin biopsy for IENFD is superficial, small, and commonly performed in patients with diabetic neuropathy, and poses minimal safety risk.

## **11.10 Risk Mitigation**

### **11.10.1 Study Level Risk Mitigation**

At the study level, risk will be mitigated through direct Investigator training, centralized safety data collection and monitoring, and periodic review of safety data by an independent DMC.

#### **11.10.1.1 Training and Data Management**

Measures specific to Investigator training and safety data management will be implemented as follows:

- Investigator and site personnel training will include a focused review of expectations for monitoring safety and implementing risk mitigation.
- Study data will be captured in real time using an EDC system, allowing for routine review of EDC data by the Sponsor’s Medical Monitor and clinical team, independent of the timing of on-site monitoring review.
- Routine on-site review of study records and data by the Sponsor’s monitoring affiliate will begin directly after the first patient is treated at each study center.

- A central clinical laboratory will be used for hematology, serum chemistry, and urinalysis to provide standardization across study centers, rapid on-line access to results, and customized alerts for results requiring exclusion/discontinuation, thereby allowing Investigators as well as the Sponsor's Medical Monitor to identify potential safety issues early; standardized reference ranges for each test will be provided on every report of results and will also be available in the laboratory manual.
- A core cardiovascular laboratory will be used to provide standardization in ECG collection and interpretation across study centers, with rapid on-line access to results and customized alerts for exclusion/discontinuation.
- SAE reports and associated data will be reviewed on an expedited basis by the Sponsor and its affiliates in order to meet reporting obligations and implement additional risk mitigation (if applicable).

#### **11.10.1.2 Data Monitoring Committee**

As described in Section 10.3.8, an independent DMC will meet periodically to perform a comprehensive review of accumulated safety data. In order to complete an informed review, the DMC will be provided with treatment assignment information for each patient (i.e., unblinded data). An independent, unblinded statistician will facilitate safety data review by the DMC.

The DMC will be provided with event and case report data on an ad hoc basis when a patient is discontinued for any of the AEs of special interest outlined in Section 11.10.2.2. As with the formal scheduled reviews, treatment assignment information will be included. The DMC will assess safety data for evolving trends, with particular attention to the events of special interest described below. As described above (Section 10.3.8) the DMC may also perform an interim analysis to assess efficacy or futility.

#### **11.10.2 Patient Level Risk Mitigation**

##### **11.10.2.1 Patient Exclusion**

Given the potential for undue risk, certain patients will be excluded from study participation as follows:

- Patients at risk for QT interval prolongation as a result of personal or family history, or with measured QTc prolongation on Screening ECG.
- Patients with any hematologic or select serum chemistry abnormalities suggesting serious, ongoing medical problems, including significant renal or hepatic impairment.
- Patients with significant comorbidities or other medical conditions, laboratory abnormalities, or psychiatric illnesses that would place the patient at increased risk.

- As the effect of ricolinostat on fetal development is not known, pregnant women or women wishing to become pregnant will be excluded from the study, as will FOCBP who do not agree to use contraception as outlined above. Breastfeeding mothers will also be excluded.

### 11.10.2.2 Adverse Events of Special Interest and Monitoring Procedure

The following AEs are designated as events of special interest, and, if observed as treatment-emergent during the study, should be addressed as described below: Anemia, leukopenia, neutropenia, thrombocytopenia, renal impairment, congestive heart failure, suicidality.

Observation	Risk Management
Clinical Laboratory Parameters for Adverse Events of Special Interest	
Cardiac Conduction: QTcF $\geq$ 500 ms or QTcF increase from baseline $\geq$ 60 ms and QTcF $\geq$ 480 ms	
 
For any observed case, the investigator should repeat the ECG assessment twice and compare the average of these 3 measurements of QTcF to the average of the 2 pre-treatment (i.e. screening and baseline) QTcF values
 
If confirmed, patient should be discontinued and appropriate follow-up instituted
 

Anemia: Hemoglobin decrease from baseline $> 2$ g/dL, or a decrease from baseline of at least 1.0 g/dL to a value below 11.5 g/dL (female) or 13 g/dL (male)	
 
For any observed case, repeat laboratory test within one week to confirm: 
 
If the abnormality persists on repeat laboratory test, refer to section 11.10.2.2.1 for additional laboratory monitoring and initiate appropriate medical work-up to assess potential causes.
 
 
 

Leukopenia: White blood cell count $< 2500/\text{mm}^3$ ; or a decrease from baseline $> 1500/\text{mm}^3$	
Neutropenia: Neutrophil count $< 1250/\text{mm}^3$ ; or decrease from baseline $> 500/\text{mm}^3$	
Platelet count $< 100,000/\text{mm}^3$ ; or a decrease from baseline $> 50,000/\text{mm}^3$	
eGFR $< 30 \text{ ml/min}/1.73 \text{ m}^2$	
 
Confirm with repeat test within one week; if confirmed, patient should be discontinued and appropriate follow-up instituted
 

C-SSRS: Response of “yes” to suicidal ideation questions 4 or 5; or response of “yes” to any suicidal behavior questions	
 
For C-SSRS response of yes to suicidal ideation items: evaluate and ensure patient’s immediate safety; ensure patient has appropriate mental health follow up and any necessary intervention to assure patient’s safety. If patient describes intent to act or formed plan (i.e., more than passive suicidal ideation), discontinue patient from study treatment, ensure appropriate mental health follow-up and schedule for safety follow-up.
 

Cardiac Function	

New onset symptomatic bradycardia observed during Treatment period; i.e., heart rate < 50 bpm with weakness, confusion, shortness of breath, chest pain or hypotension, or evidence of new onset (i.e., not previously diagnosed) congestive heart failure	

For bradycardia, repeat measurements at least 30 minutes later to confirm. For confirmed bradycardia or new onset congestive heart failure, stop study drug and initiate appropriate medical workup.

If no underlying, non-study drug-related cause can be ascertained, no further study drug should be administered, study discontinuation measures should be obtained, and the patient should be followed until resolution.

--	---

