IENFD will be studied in approximately 120 patients at a selected subgroup of investigational centers by skin biopsy during the baseline observation period and again at the end of the approximately 24 week treatment period. At each timepoint, two samples will be taken from each patient: one proximally on the lateral thigh 10 cm above the fibular head, and one distally towards the ankle 10 cm above the lateral malleolus. This sub-study will include at least 60 patients randomized to the ricolinostat group and a similar number of patients randomized to the placebo group. Based on 1:1 randomization to the study treatment arms, among 24 week completers, approximately half the sample of patients participating in the IENFD sub-study will have 24 weeks of exposure to ricolinostat and approximately half will have 12 weeks of exposure to ricolinostat, providing an opportunity to assess magnitude of change as well as time course of change in IENFD. This sub-study is exploratory and the null hypothesis of greatest interest is that the change from baseline in nerve fiber density is zero in the group receiving 6 months of ricolinostat. The power of this sample size to detect an effect is not known precisely. However, extrapolating from rates of nerve fiber regrowth in healthy subjects after capsaicin administration, assuming a moderate drug effect, and even assuming a slower rate of regeneration as compared with healthy subjects, the proposed sample is expected to provide approximately 80% power to detect an increase of 0.44 fiber/mm assuming a standard deviation of 1.2 fibers after 24 weeks of treatment. Because nerve fiber density may decrease with age, patients older than 75 years are not eligible to participate in the intraepidermal nerve fiber biopsy sub-study. To mitigate the risk that more than a simple ‘band-aid’ type dressing would be required after the biopsy, patients taking anticoagulants are not eligible for intraepidermal nerve fiber biopsy.

A study flow diagram is presented in [Figure 3](#).

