## **9.5 Treatment Period (Week 1 to Week 12)**

Following randomization on Day 1, patients will return to the clinic for visits as outlined in the schedule of events. During each visit, the procedures specified by the schedule of events for that visit will be performed.

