#### **9.5.4 Week 8**

The following procedures will be performed at Week 8:

- Administer C-SSRS (Since Last Visit version);

- Obtain vital signs (temperature, respiration rate, pulse, and blood pressure) while patient is sitting after a minimum 5-minute rest. Standing pulse and blood pressure to be obtained following sitting vital signs;
- Perform directed physical exam to assess changes from the prior visit or new concerns;
- Assess skin integrity and wound healing, if applicable;
- Collect blood sample for the following:
  - Hematology;
- Collect urine samples for the following:
  - Urine pregnancy test (if FOCBP);
  - Urine drug screen;
- Record concomitant medications and AEs;
- Collect returned study drug (used and unused bottles) and perform study drug accountability;
- Instruct patient on daily completion of NRS (worst and average pain experienced each day) and rescue medication use, as applicable (at the discretion of the Investigator); and
- Dispense study drug assigned by IRT.

At the conclusion of the 12-week Treatment period, patients will enter the Safety Extension period.

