## **9.6 Safety Extension (Week 12 to Week 24)**

From Week 12 to Week 24, all patients will receive ricolinostat 120 mg daily. Patients will return to the clinic as outlined in the schedule of events and at each visit procedures specified in the schedule of events for that visit will be performed.

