#### **10.2.1.2.2 Patient Global Impression of Change**

The PGIC is a validated tool commonly used in pain assessment (Farrar, 2001).

The PGIC is comprised of a single question administered at the end of the Treatment period (Day 28) to assess the overall quality of life since the beginning of study treatment. The answer is scored from 1 to 7 on a gradient where 1 = no change (or condition is worse), and 7 = a great deal better/considerable improvement. Examination of the PGIC scores at Weeks 4 and 12 will be a secondary study endpoint.

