#### **10.2.1.2.6 Use of Rescue Medication**

Use of rescue medication will be recorded by the patient in the daily diary beginning at the start of the Pain Observation period on Day -14 and ending on Week 12, the last day of the Treatment period, or upon premature discontinuation as applicable.

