### **10.2.2 Safety Assessments**

The following safety assessments will be performed during the study as outlined in [Table 1](#) and the data will be used for safety analyses as described in Section [10.3.7](#).

- Vital signs
- Physical examination (including skin integrity and wound healing, if applicable)
- 12-lead ECG
- Laboratory assessments (hematology, serum chemistry, and urinalysis)
- AEs

Skin integrity, the presence of wounds, and wound healing, if applicable, will be assessed Pre-Treatment (Day 1), weekly during the Treatment period and Safety Extension period, and at the final visit (Week 28). Examination of each wound, whether it was pre-existing on Day 1 or develops during the study, will include documentation of the wound's location, size, and depth along with assessment for signs of infection, such as erythema, edema, warmth, odor, or drainage. Signs of impaired healing or infection will be followed and evaluated to determine if they meet criteria for reporting as an AE.

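### Read literally, the mandatory stop rule for symptomatic bradycardia ends at Week 12, just as every patient goes onto ricolinostat; probably a drafting slip, and one phrase repairs it

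*Protocol*

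**What the plan says.** The Cardiac Function row of the table in Protocol 11.10.2.2 opens with "New onset symptomatic bradycardia observed during Treatment period". It defines the event as a heart rate below 50 bpm with weakness, confusion, shortness of breath, chest pain or hypotension. The measurement is repeated at least 30 minutes later. If it is confirmed, study drug is stopped and a work-up begins, and if no cause other than study drug is found, dosing does not resume.

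The period named in that trigger has a stated place in the visit structure. The heading of Protocol 9.5 is "Treatment Period (Week 1 to Week 12". Section 9.1 lists Treatment and Safety Extension as separate periods. Section 9.5.4 closes with "At the conclusion of the 12-week Treatment period, patients will enter the Safety Extension period". Section 10.2.1.2.6 has rescue medication recording "ending on Week 12, the last day of the Treatment period". Where both periods are meant, section 10.2.2 names both: "weekly during the Treatment period and Safety Extension period".

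On exposure after Week 12, section 9.6 says: "From Week 12 to Week 24, all patients will receive ricolinostat 120 mg daily".

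**The concern.** A rule that tells sites to confirm, stop and investigate should cover all the time a patient is on active drug. As worded, this one covers a former placebo patient only while that patient is on placebo and lapses when ricolinostat starts. A confirmed rate below 50 bpm with chest pain requires a stop at Week 8. The same finding at Week 18 is left, on the literal reading, to general provisions and to the investigator's judgement. The plan foresees about 50 sites, and different sites could handle the same event differently.

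**Working it through.** The plan states no figure on this point, so there is none to reproduce. The check compares the text and then counts exposure.

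**Text**

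1. The limit is peculiar to this row. In the same table, the QTcF, hemoglobin, white cell, neutrophil, platelet, eGFR and C-SSRS triggers carry no period limit.
2. The visit structure gives one meaning. Sections 9.1, 9.5, 9.5.4, 9.6 and 10.2.1.2.6 agree that the Treatment period ends at Week 12 and the Safety Extension follows.
3. The term is not used consistently elsewhere. Section 10.2.1.2.2 describes the PGIC as "administered at the end of the Treatment period (Day 28", and section 7.1 schedules the second skin biopsy "again at the end of the approximately 24 week treatment period". Appendix II describes C-SSRS monitoring as taking place during the Treatment period, although the schedule gives the C-SSRS at Weeks 14, 18, 24, 26 and 28. Nothing says which meaning governs the bradycardia trigger.
4. The lead-in sentence of 11.10.2.2 applies throughout the study, but to a list of events. Congestive heart failure is on that list and bradycardia is not. Heart failure therefore stays covered after Week 12 even though it shares the cell with bradycardia.

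**Exposure outside the rule, on the Week 12 meaning**

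Inputs: 274 patients (Protocol 10.3.1), 1:1 allocation (7.4.2), about 12 weeks double-blind followed by about 12 weeks open-label on ricolinostat for all (7.1, 9.6).

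- Per arm: 274 / 2 = 137.
- Ricolinostat arm: 137 × 24 = 3,288 patient-weeks.
- Placebo arm, from Week 12: 137 × 12 = 1,644 patient-weeks.
- Total planned: 3,288 + 1,644 = 4,932.
- Inside the rule: 137 × 12 = 1,644.
- Outside the rule: 274 × 12 = 3,288.
- Share outside: 3,288 / 4,932 = 66.7%.

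With equal arms the share does not depend on the number randomized: (2 × 12) / (24 + 12) = 2/3. By arm, half of the ricolinostat group's exposure and all of the former placebo group's exposure fall outside.

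Dropout lowers the share a little. Assume that a proportion d leaves evenly within each 12-week period, so that a leaver contributes 6 weeks on average. The documents give no dropout figure; 20% to 30% is an assumption.

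- d = 20%: mean weeks 0.8 × 12 + 0.2 × 6 = 10.8. Double-blind 137 × 10.8 = 1,479.6; extension 274 × 0.8 × 10.8 = 2,367.4; share 2,367.4 / 3,847.0 = 61.5%.
- d = 30%: mean weeks 0.7 × 12 + 0.3 × 6 = 10.2. Double-blind 137 × 10.2 = 1,397.4; extension 274 × 0.7 × 10.2 = 1,956.4; share 1,956.4 / 3,353.8 = 58.3%.

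**The case against.** The best case against is that nobody would read the row this way. The table's lead-in is study-wide. QTcF is also missing from the lead-in list yet has its own row, so absence from the list need not narrow a row. The qualifier may simply explain what new onset means, just as the heart failure half of the cell explains it as not previously diagnosed. On that view it separates onset after randomized treatment from onset in the placebo lead-in, when the dispensed product is also called study drug (9.3.1, 11.1.3). The loose uses of the term in section 7.1 and Appendix II support a broader sense.

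Much of this stands. It makes a drafting slip the likeliest explanation, and the documents do not show that the sponsor meant to switch the rule off. It does not settle the meaning, because this row carries an explicit limit that the QTcF row lacks, and the visit sections define that limit as Week 12.

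The second argument is that patients remain protected, and that is largely right. Section 7.7 gives grounds for discontinuation at any time, including a clinically significant adverse event and the investigator's judgement. Section 11.1.2 requires adverse events to be followed until resolved or no longer of concern. Section 11.4 adds roughly weekly visits for unresolved events. A rate below 50 bpm with chest pain or hypotension could qualify as an important medical event under 11.1.1 and be reported within 24 hours under 11.1.3. Many investigators would stop the drug anyway. What these provisions lack is the 50 bpm threshold, the 30-minute repeat and a required stop.

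Four stronger readings are tempting, and the documents support none of them:

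- *Extension patients have no cardiac protection.* The general provisions above apply, pulse is taken at Weeks 14, 18 and 24, and an ECG is scheduled at Week 24.
- *The rule ends at Day 28, because the PGIC section says so.* That section itself uses PGIC scores at Weeks 4 and 12. Its Day 28 looks like a remnant of a shorter design and has no bearing on this row.
- *A number of missed events can be stated.* The documents give no bradycardia rate.
- *Suicidality monitoring lapses too.* The C-SSRS row has no period limit and requires discontinuation when a patient describes intent or a plan. Only the explicit stop for a suicidal behavior response depends on the Treatment period wording in Appendix II.

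**Conclusion.** The point holds as a wording defect in a safety rule. On the protocol's own visit structure, the mandatory bradycardia rule stops at Week 12 while dosing continues to Week 24. On that meaning and with no dropout, 67% of planned ricolinostat exposure lies outside it; under the assumed 20% to 30% loss per period, about 58% to 62%. If the term was meant to cover all 24 weeks, the share is zero and the edit only removes doubt. These figures measure time on drug and say nothing about how often bradycardia would occur or go unmanaged. The practical effect falls mainly on Weeks 14 and 18 and on unscheduled contacts, because dosing is ending at Week 24, although the work-up would still matter there. No efficacy analysis is touched. The change should be made at the next amendment; confidence is medium, because the intended meaning of the term is not stated.

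**What to change.** In the Cardiac Function row of Protocol 11.10.2.2, replace the period qualifier on bradycardia with: *observed at any time while on study drug after randomization (Treatment period or Safety Extension)*. Keep the heart rate threshold, the 30-minute confirmation and the work-up as they are. Naming randomization keeps the placebo lead-in out, which may be what the present wording was for. As a separate minor alignment, make the same period change in the Appendix II sentence on discontinuation for C-SSRS findings.

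The cost is two phrases in the next amendment, which needs IRB approval under section 12.5, and the work-up of any case confirmed in the Safety Extension. Section 11.10.1.2 sends the DMC an ad hoc report when a patient is discontinued for an event of special interest under 11.10.2.2, so a bradycardia discontinuation in the Extension might also generate one. No scheduled visit or test is added, since pulse and the C-SSRS are already collected at Weeks 14, 18 and 24. Bradycardia need not be added to the list of events of special interest, so the corresponding SAP list (4.4.1) and table (11.1) can stay as they are.
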